7. STUDY SUBJECTS AND CLICK DEVICES

7.1. Disposition of Subjects and Devices

The disposition of subjects in the study will be tabulated overall and by clinical site. [Table 3](#) will present the number of subjects who are screen failures and the number of subjects that met each inclusion/exclusion criterion. The number of subjects enrolled, who provided valid Click results/PIS designations, included in the Evaluable analysis populations, and who terminated early from the study will be tabulated overall and by clinical site ([Table 4](#)). [Table 5](#) will present the reasons for exclusion from the Evaluable analysis populations. A listing of subjects who completed the study, terminated early from study, and the reason for early termination is included in [Listing 1](#). A subject listing of Evaluable population eligibility for all enrolled subjects and the reason(s) for exclusion will be provided ([Listing 2](#)).

The disposition of Click devices used in the study will be tabulated overall and by clinical site. [Table 6](#) and [Table 7](#) will present the number of devices which provided valid/invalid results and the reasons for the invalid result. A device listing including all valid and invalid results will be provided ([Listing 3](#)). Results of the Click Device operator control testing will be summarized ([Table 8](#)) and a separate listing of the results of the control tests will be provided ([Listing 4](#)).

7.2. Demographic and Other Baseline Characteristics

Demographic and other baseline characteristics will be summarized for all enrolled subjects and the Evaluable populations. Ethnicity, race, symptomatic status, and age category will be summarized overall and by site ([Table 9](#) and [Table 10](#)). Ethnicity is categorized as Hispanic or Latino, or Not Hispanic or Latino. Race is categorized as American Indian or Alaska Native, Asian, Native Hawaiian or Other Pacific Islander, Black or African American, White, Multi-Racial, or Unknown. In accordance with NIH reporting policy, subjects may self-designate as belonging to more than one race (Multi-Racial) or may refuse to identify a race (Unknown), the latter reflected in the Case Report Form (CRF) as “No” to each racial option. Age will be categorized as: 14 – 17, 18 – 25, 26 – 30, 31 – 35, 36 – 40, 41 – 45, 46 – 50, 51 – 55, and > 55. Continuous age will also be summarized overall and by site ([Table 11](#) and [Table 12](#)). The number and percentage of evaluable subjects who were tested positive by the Click device will be summarized by organism and age category ([Table 13](#)).

Subject-reported symptoms occurring within 7 days prior to enrollment will be summarized overall and by organism for all evaluable subjects with positive results from the Click device ([Table 14](#)).

Targeted sexual history, including history of CT, NG, and TV, will be summarized for all enrolled subjects and the Evaluable populations ([Table 15](#) and [Table 16](#)).

Summaries of medications that were started prior to enrollment and continuing at the time of enrollment will be presented by WHO Drug Anatomical codes (ATC) Level 1 and Level 2 for all enrolled subjects and the Evaluable populations ([Table 17](#) and [Table 18](#)). Summaries of genital products used within 7 days prior to enrollment will be presented by category (e.g. gel, foam, wash, etc.) and indication (e.g. contraceptive, lubricant, cleansing, etc.) for all enrolled subjects and the Evaluable populations ([Table 19](#) and [Table 20](#)).

Individual subject listings will be presented for all demographics, clinical symptoms, targeted sexual history, concomitant medications, and genital products ([Listing 5](#), [Listing 6](#), [Listing 7](#), [Listing 8](#), and [Listing 9](#)).

7.3. Protocol Deviations

A summary of subject-specific protocol deviations will be presented by the deviation category, and the type of deviation for all enrolled subjects ([Table 21](#)). All subject-specific protocol deviations and non-subject-specific protocol deviations will be included as data listings ([Listing 10](#) and [Listing 11](#), respectively).

8. PRODUCT PERFORMANCE EVALUATION

8.1. Analysis of the Primary Outcome.

8.1.1. Primary Analysis

For the primary analysis, the 2x2 contingency table comparing the results of the Click Device and PIS will be presented by organism ([Table 22](#)). Contained in the table for each organism are the number of true positives (top left), false positives (top right), false negatives (bottom left), and true negatives (bottom right) of the Click device as well as the total number of valid positive and negative results for the Click device and PIS (Total rows and columns). For each organism, the sensitivity, specificity, accuracy, PPV, and NPV of the Click device will be presented along with their 95% Wilson confidence intervals.

[Listing 12](#) will present individual product performance data for all subjects including Click result, PIS designation, and the individual comparator assay results. The listing will include subjects excluded from the Evaluable population.

8.1.2. Supplementary Analyses

A series of summaries which provide additional insight into the primary analysis will be generated.

Summaries of comparator assay results for samples where the Click device and comparator assays/PIS were discordant will be presented by organism ([Table 23](#)), by symptomatic status ([Table 24](#)), by age category ([Table 25](#)), and by Click device lot number ([Table 26](#)).

Summaries of all observed combinations of valid results among the comparator assays for all samples tested on each assay will be presented by organism ([Table 27](#)), by symptomatic status, and age category ([Table 28](#)).

The primary analysis summaries contain estimates of PPV and NPV given data observed in this study. As an exploration, hypothetical PPV and NPV estimates will be calculated for each organism using the observed sensitivity and specificity of the Click device and a range of hypothetical prevalence rates (see [Section 3.3.6](#) and [Section 3.3.7](#) for the calculation of PPV and NPV). The hypothetical prevalences (in percentages) that will be explored for each organism are: 1, 2, 5, 10, 20, 25, 30, 50. [Table 29](#) will present the resulting PPV and NPV estimates over the range of prevalences.

The number of positive, negative, and invalid Click device results will be presented by operator ([Table 30](#)). For these summaries, a device will be considered to have “Positive” result for a specimen if the test was valid and positive for any of the three organisms. A device will be considered to have a “Negative” result for a specimen if the test was valid and negative for any of the three organisms.

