3.3.2.3. Click Device

For the Click device, a valid positive/negative result for a specimen is a result where the following was reported on the Operator Diagnostic Test Result form:

- “Did the device run successfully?” was answered with “Yes”
- “...interpret the results of the test and answer the following questions” was answered with “Positive” or “Negative”.

If the Click test is invalid, the same specimen is used for a retest using a second Click device. When retests are performed, the results of the second test for all organisms are used in analyses and the initial results from the first test for all organisms are excluded (but will be included in subject listings).

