5. SAMPLE SIZE CONSIDERATIONS

Recruitment goals for the 510(k) phase of the study are at least 100 specimens positive for each of CT and TV, and at least 45 specimens positive for NG as determined by PIS. Recruitment goals for the CLIA waiver phase of the study are 120 positive specimens for each of CT, TV, and 45 NG. Approximately 585 subjects will be recruited from low-prevalence sites (one third of the 1,750) and approximately 1165 subjects will be recruited from high prevalence sites. The average expected proportion of samples positive via PIS for CT, TV, and NG among subjects enrolled at the high prevalence sites are, respectively, 12.4%, 19.5%, and 8.1%. The corresponding estimates for the low prevalence sites are 1.7%, 1.0%, and 1.4%. Based on these prevalence estimates, it is expected that the enrollment targets will be met for the three organisms. Thus, the study as designed is expected to meet the 510(k) and CLIA waiver recruitment goals for all three organisms. If NG prevalence is lower than expected, banked NG+ samples may need to be leveraged to meet the recruitment goals for NG. As indeterminate PIS designations or invalid or failed Click device results are expected for a small number of cases, enrollment may extend beyond 1750 to replace these results. The duration of enrollment may be extended if the actual prevalence of any of the organisms is lower than predicted.

For the estimation of the sensitivity and specificity of the Click device, we assume both the sensitivity and specificity is at least 95%. For 510(k) clearance, the study aims to demonstrate that sensitivity to each of CT and NG is at least 95% with a lower bound of the two-sided 95% Wilson Score confidence intervals at least 90%, and to demonstrate that sensitivity to TV is at least 95% with a lower bound of the two-sided 95% Wilson Score confidence intervals at least 85%. Regarding specificity, the study aims to demonstrate specificity to each of CT, TV, and NG is at least 95% with a lower bound of the two-sided 95% Wilson Score confidence intervals at least 90%. For the CLIA waiver, the study aims to demonstrate that both the sensitivity and specificity to each of CT, TV, and NG is at least 95% with a lower bound of the two-sided 95% Wilson Score confidence intervals at least 89%.

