6.3. Covariates, Center Effects, and Subgroups

Though the study is not designed to adequately assess product performance within subgroups, certain summaries will be presented by operator, clinical site, lot, and symptomatic status (see Section [8.2](#)).

Safety and product performance data will be both broken up and pooled across clinical sites and operators within clinical site. Though Click devices are manufactured and shipped centrally from Click Diagnostics, the sites are using standardized procedures for assessment of unsolicited adverse events, the study utilizes a

central laboratory for comparator testing, and the study is not designed to detect subgroup effects, operator and center effects are possible. See Section 8 and Section 9 for more details.

As necessary, the study Sponsor, their designated Statistics and Data Coordinating Center, and/or authorized Principal Investigators may perform additional analyses depending on the nature of the data acquired, new regulatory directives, or to respond to unforeseen contingencies during the course of the study. Such analyses and their results, including a rationale for performing said analyses, will be described in detail in the study report and/or study publication.

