Table 5: Summary of Evaluable Populations Exclusions - All Enrolled Subjects

	CT		NG		TV	
	n	%	n	%	n	%
All Enrolled Subjects	x	-	x	-	x	-
Evaluable Subjects	x	x	x	x	x	x
Non-Evaluable Subjects	x	x	x	x	x	x
Reason(s) for Exclusion ^a :						
Subject did not meet eligibility criteria	x	x	x	x	x	x
Invalid Click result	x	x	x	x	x	x
Indeterminate PIS determination	x	x	x	x	x	x
Specimens missing/untested for Click or PIS	x	x	x	x	x	x
Click specimens were not tested within 2 hours of collection	x	x	x	x	x	x
Comparator specimens tested outside the stability window	x	x	x	x	x	x
Any protocol deviation that, in the opinion of the investigators, is deemed to impact validity of assay results	x	x	x	x	x	x
Any other reason that, in the opinion of the investigators, is deemed to impact validity of assay results	x	x	x	x	x	x

Notes: Denominators for percentages is the number of enrolled subjects

^aSubjects may be counted under more than one reason for exclusion**Implementation Notes:**

Depending on the observed counts of the "Any protocol deviation..." and "Any other reason..." reasons, these rows may be combined into a single row "Any protocol deviation or other reason that, in the opinion of the investigators, is deemed to impact validity of assay results".

Table 6: Click Device Disposition for Clinical Specimens by Site

Test	Device Disposition	Reason for Invalid	Site 1 (N=X)		Site 2 (N=X)		...	All Subjects (N=X)	
			n	%	n	%		n	%
Initial Test	Valid Result		x	x	x	x	...	x	x
	Invalid Result	Any Reason	x	x	x	x	...	x	x
		Device Error	x	x	x	x	...	x	x
All Tests (initial and re-test)	Valid Result		x	x	x	x	...	x	x
	Invalid Result	Any Reason	x	x	x	x	...	x	x
		Device Error	x	x	x	x	...	x	x
		Other	x	x	x	x	...	x	x

Notes: N=Number of subjects with an initial test performed, and is used for denominator for all percentages.

For All Tests (initial and re-test) a subject is counted as having a valid result either the initial or re-test result is valid, and counted as an invalid, if result if both initial and re-test results are invalid.

Table with similar format:

Table 7: Click Device Disposition by Lot Number

Implementation Note: The columns will be the Lot Numbers and "All Lots".

Table 8: Success Rates of Click Device Operator Control Testing

Control Type	Initial Test			Re-Test		
	n	N	%	n	N	%
Negative	x	x	x	x	x	x
Positive	x	x	x	x	x	x
All	x	x	x	x	x	x

Table 9: Summary of Categorical Demographic and Baseline Characteristics by Site – All Enrolled Subjects

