Implementation Note: The first column will be Device Lot number.

Table 27: Observed Combinations of Click and Comparator Assay Results by Organism

Organism	Combination of Results					Observed Frequency	
	Click	BD Probetec	Hologic Aptima	BD Max	PIS Designation	n	%
CT (N = X)	Positive	Positive	Positive	NA	Positive	x	x
	Positive	Positive	Negative	Positive	Positive	x	x
	...Continue for all observed combinations...						
TV (N = X)	Positive	Positive	Positive	NA	Positive	x	x
	Positive	Positive	Negative	Positive	Positive	x	x
	...Continue for all observed combinations...						
NG (N = X)	Positive	Positive	Positive	NA	Positive	x	x
	Positive	Positive	Negative	Positive	Positive	x	x
	...Continue for all observed combinations...						

Note: Denominator of percentages is the number of subjects in the Evaluable population for the specified organism (N).

Table 28: Observed Combinations of Click and Comparator Assay Results by Organism and Baseline Characteristics

Characteristic	Organism	Combination of Results					Observed Frequency	
		Click	BD Probetec	Hologic Aptima	BD Max	PIS Designation	n	%
Characteristic #1	CT (N = X)	Positive	Positive	Positive	NA	Positive	x	x
		Positive	Positive	Negative	Positive	Positive	x	x
	...Continue for all observed combinations...							
	TV (N = X)	Positive	Positive	Positive	NA	Positive	x	x
		Positive	Positive	Negative	Positive	Positive	x	x
	...Continue for all observed combinations...							
Characteristic #2	NG (N = X)	Positive	Positive	Positive	NA	Positive	x	x
		Positive	Positive	Negative	Positive	Positive	x	x
	...Continue for all observed combinations...							
Characteristic #2

Note: Denominator of percentages is the number of subjects in the Evaluable population for the specified characteristic and organism (N).

Implementation Notes: The Characteristics that will be included in the table are:

- Symptomatic status (Symptomatic, Asymptomatic)
- Age Category (Age categories displayed in Table 7)

Table 29: PPV and NPV Estimates across Range of Hypothetical Prevalances by Organism

Hypothetical Prevalence (%)	CT		TV		NG	
	PPV	NPV	PPV	NPV	PPV	NPV
1	x.x	x.x	x.x	x.x	x.x	x.x
2	x.x	x.x	x.x	x.x	x.x	x.x
5	x.x	x.x	x.x	x.x	x.x	x.x
10	x.x	x.x	x.x	x.x	x.x	x.x
20	x.x	x.x	x.x	x.x	x.x	x.x
25	x.x	x.x	x.x	x.x	x.x	x.x
30	x.x	x.x	x.x	x.x	x.x	x.x
50	x.x	x.x	x.x	x.x	x.x	x.x

Table 30: Click Device Results by Operator

Click Device Result	Operator 1	Operator 2	...	Operator K
Positive	x	x	...	x
Negative	x	x	...	x
Invalid	x	x	...	x
Total	x	x	...	x

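### SAP 8.1.2 uses *any* in both row definitions of Table 30, so read literally a specimen positive for one or two organisms counts as both Positive and Negative

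*SAP*

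**What the plan says.** SAP 8.1.2 plans a count of positive, negative and invalid Click results for each operator and defines the rows at specimen level. A device result is Positive "if the test was valid and positive for any of the three organisms". The next sentence defines a Negative "result for a specimen if the test was valid and negative for any of the three organisms".

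The shell in SAP Appendix 1, "Table 30: Click Device Results by Operator", has one column per operator and the rows Positive, Negative, Invalid and Total. It has no footnote. No other section of the SAP or protocol redefines Negative for this table.

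**The concern.** One specimen yields three results (CT, TV, NG). A class called Positive if at least one is positive is complemented by a class in which all are negative. The SAP instead uses *at least one negative* as the other class, so the two overlap.

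This sentence is the programming specification for the only planned table that shows clinical-specimen results by operator. If it is programmed as written, a reader will take the Negative row for the number of specimens in which the operator found nothing, and that number will be too high. The planned listings do not allow a correction at operator level: Listing 3 (device results) and Listing 12 (product performance) have no operator column, and Listing 4 covers control tests only.

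**Working it through.** **Step 1: the definitions.** The plan states no figure to reproduce here. There are 2³ = 8 valid result patterns.

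| Organisms positive | Patterns | Positive row | Negative row, as written | Negative row, if *all* |
|---|---|---|---|---|
| 3 | 1 | yes | no | no |
| 2 | 3 | yes | yes | no |
| 1 | 3 | yes | yes | no |
| 0 | 1 | no | yes | yes |

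As written, six of the eight patterns fall in both rows. With *all*, none does: seven patterns are Positive and one is Negative. This step needs no assumption.

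**Step 2: inputs for the size.** From SAP 5: 1,165 subjects at high-prevalence sites (CT 12.4%, TV 19.5%, NG 8.1%) and 585 at low-prevalence sites (CT 1.7%, TV 1.0%, NG 1.4%). Sensitivity and specificity are assumed to be at least 95%. My assumptions are that all 1,750 results are valid and that no banked specimens are used. Co-infection is not given, so I use independence within site type and then one alternative.

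**Step 3: formulas.** Within a site type of size n, let a be the probability of no positive result and t the probability of three positives.

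- All-negative specimens: n·a
- Negative row as written: n·(1 − t)
- Specimens in both rows: n·(1 − a − t)
- Overstatement: specimens in both rows ÷ all-negative specimens

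**Step 4: perfect test, independent infections.**

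- High: a = 0.876 × 0.805 × 0.919 = 0.6481; t = 0.124 × 0.195 × 0.081 = 0.00196. All-negative 755.0; Negative row 1,162.7; in both 407.7.
- Low: a = 0.983 × 0.990 × 0.986 = 0.9596; t ≈ 0. All-negative 561.3; Negative row 585.0; in both 23.7.
- Together: 1,747.7 instead of 1,316.3; 431.4 ÷ 1,316.3 = +33%. The Positive row is 433.7, so Positive + Negative = 2,181 for 1,750 specimens.

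**Step 5: 95% sensitivity and specificity.** The probability of a positive result is 0.95p + 0.05(1 − p) = 0.05 + 0.9p, with test errors also taken as independent across organisms.

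- High: 0.1616, 0.2255 and 0.1229 for CT, TV and NG. All-negative 663.5; in both 496.3 (+75%).
- Low: 0.0653, 0.0590 and 0.0626. All-negative 482.3; in both 102.5 (+21%).
- Together: 1,744.6 instead of 1,145.8; 598.8 ÷ 1,145.8 = +52%.

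**Step 6: perfect test, every NG infection in a CT-infected woman, TV independent.**

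- High: a = 0.876 × 0.805 = 0.7052; t = 0.081 × 0.195 = 0.0158.
- Low: a = 0.983 × 0.990 = 0.9732; t = 0.014 × 0.010 = 0.00014.
- Together: all-negative 821.5 + 569.3 = 1,390.8; Negative row 1,750 − 18.5 = 1,731.5; 340.7 ÷ 1,390.8 = +24%.

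**The case against.** The strongest reply is that nobody would program this literally. In clinical usage, negative for any organism often means that none was found, and a Positive/Negative/Invalid/Total layout fits exclusive rows. That is a fair account of the probable intent, and it is why this is a wording error and not a flawed analysis. It does not remove the point. The same word, one sentence earlier, plainly means *at least one*. The SAP preface also says that departures from the SAP will be described and justified, so a silent correction is not the clean route either.

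It is also fair that little hangs on the table. It contains counts only, with no intervals or tests. If Total counts each specimen once, the all-negative count is Total − Positive − Invalid.

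A reader might infer more than the documents support:

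- **That retests make the unit of count undefined.** SAP 3.3.2.3 says "If the Click test is invalid, the same specimen is used for a retest using a second Click device". It then directs that the second test's results are used in analyses and the first test's excluded. That already gives one final result per specimen, and a footnote to Table 30 would largely repeat it.
- **That accuracy by operator was promised and is missing.** SAP 6.3 says "certain summaries will be presented by operator, clinical site, lot, and symptomatic status" and refers to 8.2, which has no operator breakdown. It also says "Safety and product performance data will be both broken up and pooled across clinical sites and operators within clinical site" and refers to Section 8, which contains Table 30. Protocol 7.4.3 asks for accuracy overall, by site and by symptomatic status, not by operator. The reference to 8.2 needs only an editorial correction.
- **That Table 30 certifies the minimum of five positive and five negative specimens per operator (SAP 4.1).** An operator with only five single-organism positives would indeed show 5 and 5, but neither document gives the table that function.
- **That the overstatement has firm limits.** With a perfect test, nested infections give 9% and mutually exclusive infections 39%. Those limits fail once test errors are allowed, as step 5 shows. The exclusive extreme also conflicts with Protocol 2.1, which says chlamydia and gonorrhea often occur together.

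**Conclusion.** The point holds as a minor defect in a stated counting rule. Taken literally, the SAP puts every specimen with one or two positive organisms in both rows of Table 30. That follows from the definitions alone.

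The size is illustrative: about +24% to +33% with a perfect test under the two co-infection assumptions shown, and about +52% at 95% sensitivity and specificity under independence. These figures rest on the SAP's planning prevalences and on co-infection assumptions that the documents do not supply. The excess is larger at high-prevalence sites.

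The Positive and Invalid rows are correct as defined. Sensitivity, specificity, accuracy, PPV and NPV are defined per organism in SAP 3.3.4 to 3.3.8 and do not use this classification, so no performance estimate changes.

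**What to change.** In SAP 8.1.2, define a Negative device result for Table 30 as one that is valid and negative for all three organisms. The Positive definition stays. With step 4's inputs the rows then become about 434 Positive and 1,316 Negative, which sum to 1,750.

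The cost is one word, with no new data and no new table. While the text is open, the SAP 6.3 reference to 8.2 can be extended to name Table 30 in 8.1.2; this is editorial only.

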8.2. Analysis of the Secondary Outcome

For each organism, contingency tables and estimates of sensitivity, specificity, accuracy, PPV, and NPV of the Click device will be presented by clinical site ([Table 31](#)), symptomatic status ([Table 32](#)), age category ([Table 33](#)), and Click device lot number ([Table 34](#)). [Table 35](#) will present a simplified summary of the symptomatic status analyses.

